Participants will be informed verbally and in writing during the consent process that mandatory reporting laws will be followed. Subjects who indicate current danger to themselves or others during the study will be escorted to the emergency room or Urgent Care services, both of which are located in the same building as the Department of Psychiatry.

Given the sensitive nature of information being collected, all data will be protected by a Certificate of Confidentiality and identified using unique ID numbers assigned to participants specifically for this project. Names and identifying information required for follow-up reminders will always be kept separate from research data and will not be used as study data. Text messages will only be sent with participant permission. To protect participants' privacy, communication sent via text message will be limited to scheduling [e.g., "We have you scheduled for a research appointment tomorrow (date) at (time). To confirm, text YES. To decline, text NO."]; participants' phone numbers will not be stored on research staff phones; research assistants will permanently delete all texts and calls at least once per month; and the name of the study will not be mentioned in any text. Informed consent papers will be stored in a locked filing cabinet in a locked office that is accessible only to project staff. Computerized survey data will be stored electronically on a password-protected server. Digital audio recordings of treatment sessions, which will be used to determine treatment fidelity, will be stored on password-protected computers to which only project staff will have access. All research staff will be trained in procedures for maintaining data and participant confidentiality.

Data safety and monitoring plan. [name] will monitor procedures to ensure that they conform to the approved protocol. Specifically, she will monitor (a) the progress of the research, including participant recruitment and retention and assessments of data quality; (b) adverse events and procedures for making determinations that

there may be a change to the benefit-to-risk ratio of research participation; and (c) procedures to protect participant privacy and confidentiality. She will monitor all serious, unexpected, and other adverse or potentially adverse events. Serious adverse events include those resulting in death, inpatient hospitalization, a threat to life, persistent or significant disability or incapacity, congenital anomalies/birth defects, or serious health risk. Unexpected adverse events are those that were unforeseen based on the anticipated potential risks outlined in the study protocol and informed consent. Other adverse or potentially adverse events include those that may be causally related to study participation and lead to participant distress or drop-out.

[name] will monitor data quality and adverse events on an ongoing basis and discuss these issues with the research team during weekly meetings. All serious and unexpected adverse events will be reported to the IRB within 24 hours of receipt of information. Other adverse or potentially adverse events will be monitored and reported at annual continuing reviews.

An independent, four-member Data Safety Monitoring Board (DSMB) will also be assembled to oversee the study. The DSMB will include investigators, a medical monitor, and a biostatistician who are independent of the study. Members will include those with expertise in AUD, chronic insomnia, sleep medicine, and cognitive-behavioral therapy. All DSMB members must attest that they have no conflicts of interest. The DSMB will meet once via conference call at the beginning of the study to review the study protocol, informed consent form, and monitoring plan, with emphasis on data integrity and patient safety issues. Following this initial meeting, the DSMB will meet every 6 months to review progress reports. DSMB reports will include interim statistical analyses. Any changes to these procedures that are recommended by the DSMB will be adopted. The DSMB will review adverse events and monitor study results, focusing on efficacy, recruitment progress, randomization, compliance, retention, protocol adherence, operating procedures, forms completion, intervention effects, participant safety, and minority inclusion. The DSMB will ensure adequate protection of human subjects and address ethical concerns based on Federal Guidelines. It will also make recommendations to NIH and the PI to continue or conclude the study. Discontinuation of any component of the study could be recommended for any of the following reasons: (1) compelling evidence from this study or another study of a serious adverse effect of study treatment that has potential to override potential benefit, (2) compelling evidence from this or another study of a significant beneficial effect of study treatment, such that continued denial to other groups would be unethical, and (3) low probability of addressing study aims within a feasible time frame.

9. Benefits

Participants in the CBT-I and Sleep Hygiene conditions may benefit from the sleep-related information provided. Participants may also appreciate the opportunity to engage in research that may help others benefit from treatment. Beyond these potential benefits to subjects, this research is expected to inform future research and clinical efforts to treat insomnia and reduce the consequences associated with alcohol use among returning Veterans. As noted above, we believe the risks of this research to participants are minimal and the overall benefits of this research to subjects and society outweigh these risks.

10. Payment and Remuneration

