As of April/May of 2022, BuildClinical will manage all digital marketing recruitment for this study. BuildClinical is a data-driven digital marketing company that helps academic researchers recruit participants for research studies more efficiently using social media, software, and machine learning. They will ensure that all IRB-approved guidelines and procedures are followed during recruitment. They use study-specific advertisements to engage participants on digital platforms such as Facebook, Google, WebMD, etc. Participants who click on the advertisements will be redirected to a study-specific landing page. On the landing page, the person can complete an online pre-screen questionnaire. Pre-screening data is then routed to BuildClinical's Secure Socket Layer (SSL) software, which encrypts all information to keep it private and HIPAA compliant. Their backend servers are stored in secure data centers in the USA.

Interested individuals will have the option of (a) completing the screening survey online, either via Qualtrics or BuildClinical, or (b) calling project staff to learn more about the study. In CBT-I trials with Veterans, attrition rates have ranged from 19 to 38% (Edinger et al., 2009; Germain et al., 2014; Karlin, Trockel, Spira, Taylor, & Manber, 2015). Estimating an attrition rate of 35%, we will recruit 68 participants over 34 months to obtain a final sample of **44 participants**. Approximately 9% of Veterans are women and 12-15% have PTSD; therefore, randomization will be stratified by gender and PTSD.

Screening. Individuals who are interested in the study will complete a brief eligibility screen online from remote locations and provide their first name, phone number, and email.

A research assistant will contact those who provide this information to explain the study in more detail and, if they are still interested, schedule them for the baseline assessment. Interested individuals whose only barrier to participation is travel/in-person appointments will be scheduled for a remote baseline visit.

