Initial baseline assessment visit. Individuals who are eligible and interested will be scheduled for the baseline assessment, during which they will provide informed consent. Mailing addresses will be collected during the consent process to allow us to send written communication (e.g., thank you notes, reminder letters). If participants come in person, they will provide a urine drug sample to verify self-reported illicit drug use. Redwood Toxicology 5-panel urine drug screens test for cocaine, THC, methamphetamine, opiates, and benzodiazepines. Cups come with test strips in the specimen lids, allowing for safe and efficient drug screening. A trained research assistant will take the participant's height and weight. Participants will then complete parts of the Mini International Neuropsychiatric Interview (MINI) and a Timeline Followback (TLFB) with a graduate research assistant who has been trained in clinical interviewing and assessment. Participants will complete self-report baseline measures by computer. If participants are in person, they will also wear a holter monitor/electrocardiogram, which will be used as an index of autonomic nervous system regulation, in two separate 5-minute sessions. After assessments are complete, the research assistant will orient participants to the actiwatch (Philips Respironics) and sleep diary. Procedures for remote visits will differ as follows: (a) participants will provide written consent electronically using Qualtrics, (b) participants will be unable to provide a urine drug sample, complete computerized cognitive tasks, or wear the holter monitor, and (c) an actiwatch will be mailed to participants who agree they will send it back, along with pre-stamped and addressed return postage.

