If participants endorse suicidal ideation during the baseline assessment (or at any assessment throughout the protocol), the research assistant will assess their suicidal ideation using the Columbia Suicide Severity Rating Scale. All risk information will be shared in real time with the supervising licensed clinical psychologist, who will make a clinical judgment regarding the continued level of care required. If the participant endorses active suicidal ideation with current intent and plan and is meeting with research staff in person, they will be escorted to the Psychiatric Center's Emergency Room for an in-person, comprehensive evaluation. If they endorse active suicidal ideation with current intent and plan during a remote meeting (phone call or video conference), then research staff will call 911 and provide the participant's current address to help ensure their safety. Participants who report passive thoughts of suicide (i.e., thoughts of death/dying without intention or plans for suicide) will be included in the study if they meet all other eligibility criteria.

Individuals who become emotionally distressed during assessments will remain with the trained graduate research assistant or on-site licensed clinical psychologist until they are calm. If they are included in the study, they will be encouraged to contact their interventionist or the licensed supervising psychologist if they experience emotional distress while participating in the study.

All participants who are excluded from the study will be provided with feedback on their sleep, recommendations on the treatments that might be appropriate for them (e.g., individuals reporting circadian rhythm disorders will be encouraged to maintain a consistent sleep/wake schedule), and a list of community and online resources for sleep and mental health treatment (see section 12 of the protocol below).

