At-home assessment. Participants who report symptoms of sleep apnea and attend baseline in person will be asked to wear the holter monitor/electrocardiogram (SpaceLabs Healthcare EVO device) for one night in their own homes and in their own bed to rule out diagnosis of sleep apnea. The research assistant will prepare eligible participants who screen positive for sleep apnea for this assessment using SpaceLabs Healthcare EVO devices. Monitoring will be completed in accordance with recommendations for sleep assessment (Stein & Pu, 2012). HRV monitoring will provide an index of autonomic arousal (which has been linked to sleep impairment) and an apnea hypopnea index (a measure of sleep apnea). Participants who demonstrate an apnea hypopnea index greater than 15 will be referred for polysomnography and treatment of sleep apnea.

All participants will also be asked to wear the actiwatch 24/7 and complete two full weeks of daily sleep diaries to confirm diagnosis of insomnia (>30min sleep onset latency or wake after sleep onset 3+ nights per week). Sleep diaries will be collected electronically and time-stamped each morning using the Qualtrics data management system. Participants will be asked to complete the diary each morning before noon. Those who have not completed the diary by noon will receive a reminder text or phone call from study staff.

Randomization. Participants who are eligible based on the at-home assessment will be randomized to the CBT-I or sleep hygiene only conditions.

Table 1. Assessment, therapy, and payment schedule

Week	Assmt	CBT-I	Paymt	Bonus
1	BL		30	
2		S1	20	20
3		S2		
4	Mid-tx	S3	20	
5		S4		
6	Post-tx	S5	20	
7		(S6)	30	30
8				
9				
10				
11				
12				
13				
14				
15				
16				
17				
18				
19				
20	3mo		50	
21			40	40

Note. 1mo = 1-month. Assmt = assessment. BL = baseline. Bonus = bonus payment (for completion of all previous 14 days of sleep diaries). Paymt = standard payment. Tx = treatment.

Return baseline assessment visit. Participants will be informed of their condition following the two weeks of at-home assessment. During their return visit, one of the research assistants will also provide all participants with a one-page handout on sleep hygiene, which will include personalized normative feedback on their alcohol use. The research assistant will walk the participant through the sleep hygiene handout and answer any questions they may have about the information.

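### Enrolled remote participants who report sleep apnea symptoms have no stated route to apnea evaluation

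*Combined protocol and SAP*

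**What the plan says.** All of the relevant procedures are in Section 4, Study Procedures.

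- **Screening** opens a remote entry route: "Interested individuals whose only barrier to participation is travel/in-person appointments will be scheduled for a remote baseline visit".
- **Initial baseline assessment visit** lists how remote visits differ. Among the differences, "participants will be unable to provide a urine drug sample, complete computerized cognitive tasks, or wear the holter monitor". An actiwatch is mailed, but no replacement for the holter is given.
- **At-home assessment** restricts the overnight test: "Participants who report symptoms of sleep apnea and attend baseline in person will be asked to wear the holter monitor/electrocardiogram". Its purpose is given as "for one night in their own homes and in their own bed to rule out diagnosis of sleep apnea".
- The same paragraph sets the consequence: "Participants who demonstrate an apnea hypopnea index greater than 15 will be referred for polysomnography and treatment of sleep apnea". It names the heart-rate-variability monitoring as what supplies the index.

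Two other places offer advice or referral. Under the baseline visit, "All participants who are excluded from the study will be provided with feedback on their sleep, recommendations on the treatments" that might suit them, together with "a list of community and online resources for sleep and mental health treatment". Under Risks (Discomfort), referrals are offered when participants report distress. Section 5 does not list sleep apnea or its symptoms as an exclusion.

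**The concern.** The protocol's own position is that an AHI above 15 calls for a sleep study and treatment. It asks about apnea symptoms and follows them up for people who come to the clinic. For people seen remotely, the visible text has no follow-up step.

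The stake is participant care. CBT-I here includes restricting time in bed, and the Risks section names temporary daytime fatigue as an effect of doing so. A remote participant with unrecognised apnea could go through that restriction without being told to have the symptoms checked. The five-hour floor on time in bed and the advice on staying alert reduce the fatigue risk, but neither directs anyone to evaluation.

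**Working it through.** No sample size, power or error rate is involved, so the check is a trace through the text.

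**Step 1. Can a remote participant be enrolled?** Yes, by the remote baseline visit (Screening). The payment table under Follow-up assessments also lists the baseline clinical interview as held by Zoom, so remote entry may be common.

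**Step 2. Can that participant have the overnight test?** No. The test is limited to in-person attendees (At-home assessment), and the remote-visit list says that the holter cannot be worn. A later sentence, on preparing eligible participants who screen positive, does not repeat the in-person condition. It refers back to the same assessment, however, so it does not widen access.

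**Step 3. Can the referral be triggered?** The trigger is an AHI above 15. The referral sentence does not mention visit mode. The index has one stated source, the holter recording, so no holter means no index and the trigger cannot be met. The dependence on in-person attendance is indirect.

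**Step 4. Is there another stated route?**

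| Route | Who it covers | Covers an enrolled remote participant with apnea symptoms? |
|---|---|---|
| Sleep feedback, treatment recommendations, resource list (baseline visit) | People excluded from the study | No |
| Referrals (Risks, Discomfort) | Participants reporting distress | Not on account of apnea symptoms |
| Exclusion criteria (Section 5) | Apnea not listed | Does not move them into the excluded group |

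**Step 5. Does it matter whether an AHI above 15 bars randomisation?** The text is ambiguous. The rule-out purpose of the test, and randomisation being conditional on eligibility at the at-home assessment, point towards a bar. The silence of Section 5 points away from one. If there is a bar, a remote participant has no index to trigger it and so does not reach the advice for excluded people. If there is none, the in-person participant with a high index is referred and the remote one is not. The gap is present under both readings.

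**Step 6. Size.** The number affected is N × (remote share) × (share of remote participants with symptoms). The documents give neither share. N is also unclear: 44 is described both as the number randomised and as the final sample after 35% attrition from 68 recruits (68 × 0.65 = 44.2). Any count would reflect the shares chosen for it, so none is offered.

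**The case against.** **The text is incomplete.** Figure 1, most of Section 12 and the consent pages are not visible, and apnea advice could sit in any of them. This stands as a limit: the finding concerns the visible text only. What can be seen describes the Section 12 list as something given to excluded people.

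**Oversight may catch cases.** Patient interactions are supervised weekly by a licensed psychologist, who is in turn supervised by a psychologist certified in behavioral sleep medicine. Session recordings are reviewed, after-hours support exists, and the DSMB includes a medical monitor and sleep medicine expertise. These make an unnoticed case less likely. None is tied to apnea symptoms, so none is a stated route.

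**A remote counterpart was not necessarily owed.** The protocol does adapt suicide-risk procedures for remote contact ("during a remote meeting (phone call or video conference), then research staff will call 911"), but that is an emergency measure and does not show that apnea screening needed the same. This is fair, and the finding does not rest on the analogy. It rests on the protocol's own view that a high AHI needs follow-up.

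**Little may remain to change.** This is version 13, dated 12/29/2022, and participants were already enrolled by early 2021 in a planned 34-month recruitment. Few baselines may be left. That is a reason to reach current participants too.

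**Stronger readings to avoid.** A reader might infer that the protocol expressly denies referral to remote participants. It does not; the restriction follows from where the index comes from. A reader might also infer that the trial result is biased. Visit mode and reported symptoms both precede randomisation, so the gap applies to both arms alike and does not bias the comparison of CBT-I with sleep hygiene.

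**Conclusion.** The point holds for the visible text. Followed as written, the procedures leave enrolled remote participants with apnea symptoms without a stated path to the evaluation that the protocol provides for their in-person counterparts. It is worth correcting as a cheap safety improvement. No estimand, analysis or conclusion of the trial changes.

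The conclusion assumes that the holter is the only source of the AHI, as the text indicates, and that the parts not visible contain no apnea route for enrolled remote participants. The size of the group is unknown.

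**What to change.** Add one item to the list of remote-visit differences under Initial baseline assessment visit: *(d) remote participants who report symptoms of sleep apnea will be advised at the baseline visit to seek sleep apnea evaluation and will be given the section 12 resource list.* Tell symptomatic remote participants who are already enrolled at their next contact. If staff already do this, the amendment simply records it. The same amendment is a convenient place to state whether an AHI above 15 bars randomisation.

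The cost is one sentence through the IRB and some extra copies of an existing handout. No new test, exclusion, data item or analysis is needed. Someone should check that the list helps a remote participant find apnea testing, since most of it is not visible here.

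There are two downsides:

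- The advice is triggered by symptoms and not by an AHI, so some remote participants without apnea will be told to seek testing. Symptomatic in-person participants would still be referred only above 15.
- A few people may start apnea treatment during follow-up. For new participants the advice precedes randomisation and so cannot differ by arm. Uptake comes later and may differ, because CBT-I participants have weekly one-hour sessions and sleep hygiene participants have weekly check-in calls. For those already enrolled, the advice itself comes after randomisation.

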Date: 12/29/2022

Version Number: 13

Principal Investigator: [name] [name]

Application Number: 2014239

Application Title: The Impact of Insomnia Treatment on Heavy Alcohol use among Returning Veterans (Project iTAP for Veterans)

Protocol

1. Abstract

Heavy alcohol use is prevalent among returning Veterans and results in significant physical and psychological burden. One in five returning Veterans screens positive for probable past-year alcohol use disorder (AUD), and few hold positive beliefs about mental health treatment. Moreover, brief interventions for alcohol use demonstrate limited efficacy within this population. Thus, additional strategies are needed to engage and treat returning Veterans who may be at risk for AUD. More than half of returning Veterans who screen positive for hazardous drinking report clinically significant symptoms of insomnia. In turn, insomnia symptoms have been associated with increased risk of alcohol-related problems, perhaps due to insomnia-related impairments in executive functioning, negative emotionality, craving for alcohol, and use of alcohol as a sleep aid. The proposed K23 aims to determine the utility of the first line of treatment for insomnia (Cognitive Behavioral Therapy for Insomnia or CBT-I) in reducing alcohol use and related problems among Veterans of the Operation Enduring Freedom (OEF), Operation Iraqi Freedom (OIF), and Operation New Dawn (OND) era. Forty-four Veterans who report heavy drinking ($\geq 4/5$ drinks per occasion for women/men) and have insomnia based on DSM-5 and research diagnostic criteria will participate in a randomized pilot trial. Participants will be randomly assigned to receive personalized normative alcohol feedback in the context of one of two treatment conditions: CBT-I (n = 22) or a sleep hygiene education control (SH; n = 22). Outcomes will be assessed at the end of the active intervention period (6 weeks), mid-treatment (after 3 sessions), post-treatment, and at 3 months post-intervention. Outcomes of interest include insomnia severity, total wake time, sleep quality, drinking quantity/frequency, alcohol-related consequences, executive functioning, negative affect, emotion regulation, craving for alcohol, and use of alcohol as a sleep aid.

2. Objectives (include all primary and secondary objectives)

- (1) To evaluate the feasibility and acceptability of CBT-I among heavy-drinking Veterans.

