Follow-up assessments. To enhance follow-up rates, participants will receive up to \$300 for completion of all phases of this study. The proposed payment schedule is as follows:

Baseline		Up to \$70
Clinical interview (Zoom)	60-90min	\$0
Online survey	30-45min	\$30
14 days of actiwatch	---	\$20
14 consecutive diaries	2-3min/day	
-7 in a row to be eligible		needed for eligibility, \$0 bonus
-10 in a row		\$10 bonus
-14 in a row		\$20 bonus
Mid-Treatment		Up to \$20
Online survey	10-15min	\$20
Post-Treatment		Up to \$80
Online survey	30-45min	\$20
-phone only	5min	\$10
14 days of actiwatch	---	\$30
14 consecutive diaries	2-3min/day	

-7 in a row		\$10
-10 in a row		\$20
-14 in a row		\$30
3-Month Follow-Up		Up to \$130
Online survey	30-45min	\$50
-phone only	5min	\$20
14 days of actiwatch	---	\$40
14 consecutive diaries	2-3min/day	
-7 in a row		\$10
-10 in a row		\$20
-14 in a row		\$40

Participant retention. To enhance follow-up rates, participants will receive up to \$70 for completion of the baseline, \$20 for the mid-treatment assessment, up to \$80 for the post-treatment assessment, and up to \$130 for the 3-month follow-up; for a total of up to \$300. They will also receive reminder texts/calls, have access to free parking outside the research lab, receive immediate payment, and have access to after-hours ‘on-call’ support. We will also send all participants a personalized “thank you” note following study completion.

Blinding. [name] will not be blinded to block size or participant assignment because she will inform study therapists of participant assignment to conditions. However, [name] and study therapists will be blinded to assessment outcomes, and the assessment RA will be blinded to participant condition. All participants will be told that they are receiving treatment for insomnia in order to blind them to condition assignment (sleep hygiene will be described as “brief” insomnia treatment, and CBT-I will be described as the “most intense” treatment).

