Individuals will be excluded if they are unable to provide informed consent, report contraindications for CBT-I (mania or seizure disorder), work on a rotating shift schedule, have a severe or untreated psychiatric disorder that requires immediate clinical attention (e.g., psychosis, suicidal ideation with intent and plan), or are already receiving behavioral treatment for insomnia.

6. Drugs/ Substances/ Devices

N/A

7a. Primary Outcomes

Recruitment. Completion of 1+ session of CBT-I will be used to indicate recruitment.

Retention. Completion of all sessions of CBT-I will be used to indicate retention.

Client Satisfaction Questionnaire. The Client Satisfaction Questionnaire (Larsen, Attkisson, Hargreaves, & Nguyen, 1979) is an 8-item measure of satisfaction with treatment that has been validated in substance use treatment settings (Kelly et al., 2018). Items are scores from 1 to 4, with higher scores indicating greater satisfaction with treatment. For example, response options for the item, “How would you rate the quality of services you received?” range from 1 (poor) to 4 (excellent).

Timeline Followback. The Timeline Followback (TLFB) will be used as a face-valid measure of change in drinking quantity and frequency from baseline to follow-up (Sobell & Sobell, 1996). Using a calendar-based form, participants will indicate how many standard drinks they consumed on each day over the past 6 weeks. Holidays and significant historical events will be labeled to enhance memory recall. The TLFB will be used to estimate percentage of abstinent days and percentage of heavy-drinking days (4/5+ drinks for women/men).

Brief Young Adult Alcohol Consequences Questionnaire. The Brief Young Adult Alcohol Consequences Questionnaire (BYAACQ) is a 24-item measure of alcohol-related problems that has demonstrated reliability and concurrent validity among young adults who drink alcohol (Kahler, Hustad, Barnett, Strong, & Borsari, 2008; Kahler, Strong, & Read, 2005). Participants indicate (yes/no) if they have experienced consequences such as saying/doing embarrassing things, taking foolish risks, drinking on nights they had planned not to drink, or passing out from drinking in the past 30 days. Possible total scores range from 0 to 24.

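### One team member may know the block size although her stated task needs only the assignments; if blocks are fixed, some upcoming allocations could be known in advance

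*Combined protocol and SAP*

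**What the plan says.** Section 4, Blinding, states that one member of the study team (name removed) "will not be blinded to block size or participant assignment because she will inform study therapists of participant assignment to conditions". The same paragraph keeps that person and the therapists unaware of assessment results, and keeps the assessment research assistant unaware of condition.

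Section 4, Recruitment, adds that "randomization will be stratified by gender and PTSD", and gives the expected mix: "Approximately 9% of Veterans are women and 12-15% have PTSD". It also gives the numbers: "Estimating an attrition rate of 35%, we will recruit 68 participants over 34 months", for a final sample of 44. The Abstract splits these 22 and 22, so allocation is 1:1.

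Section 4, Randomization, says only that people found eligible after the home assessment are randomized. The text available for review states no block size, no choice between fixed and varying blocks, no holder of the list and no method of concealment.

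**The concern.** The access granted is wider than the reason given for it. Telling a therapist which condition a participant has been given requires one fact, available after the event. Block size serves a different purpose: together with the past assignments in a stratum, it shows what remains in the current block. In a fixed 1:1 block the last place is always known, and sometimes earlier places are too.

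The stated blinding measures protect outcome assessment. None of them protects the next allocation. If anyone who can foresee an allocation can also influence who enters, the arms may differ at entry in ways that were not measured. The covariate rule in section 8 (Data analysis) adjusts for listed baseline variables related to both group and outcome. It cannot reach unmeasured differences.

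**Working it through.** **Inputs from the protocol.** Allocation 1:1; strata gender by PTSD, taken as 2 × 2 = 4; 9% women; 12-15% with PTSD; final N = 44; 68 recruited.

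**Assumptions.** Blocks are fixed at 2, 4 or 6. Gender and PTSD are independent.

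**The plan's own figures.** The plan gives no figure for predictability. Its sample sizes reproduce. For f = .25, with 4 repetitions and correlation .40, the noncentrality is N·f²·m/(1−ρ) = 44 × .0625 × 4/.60 = 18.3 on 3 and 126 degrees of freedom, which gives power .957. Attrition: 44/(1 − .35) = 67.7, so 68.

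**Complete blocks.** An allocation is forced once one arm's places in the block are used up, so the number forced equals the length of the final run of identical assignments.

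- Block of 2: 2 sequences, 1 forced place each; 2/(2 × 2) = 50%.
- Block of 4: 6 sequences; 4 end in a run of one and 2 in a run of two; (4 + 4)/(6 × 4) = 33%.
- Block of 6: 20 sequences; 12, 6 and 2 end in runs of one, two and three; (12 + 12 + 6)/(20 × 6) = 25%.

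In general the share is 1/(b/2 + 1). The best-guess hit rate, choosing the arm with more places left, is 75%, 71% and 68%, against 50% with no information.

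**With strata.** At N = 44 and 12% PTSD the expected strata are:

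- men without PTSD: .91 × .88 × 44 = 35.2
- men with PTSD: .91 × .12 × 44 = 4.8
- women without PTSD: .09 × .88 × 44 = 3.5
- women with PTSD: .09 × .12 × 44 = 0.5

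At 15% PTSD they are 34.0, 6.0, 3.4 and 0.6. Unfinished blocks lower the forced share. Simulation (2,000 runs per setting) gives:

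| Fixed block size | Certain, N = 44 | Best guess, N = 44 | Certain, N = 68 |
|---|---|---|---|
| 2 | about 21 (48%) | 74% | about 33 (49%) |
| 4 | about 13 (30%) | 69% | about 21 (31%) |
| 6 | about 9 (21%) | 66% | about 15 (22-23%) |

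**After the change.** Block sizes vary at random (4/6 or 2/4/6 assumed), the sizes in use are withheld, and the guesser picks whichever arm is behind in the stratum. Certain allocations fall to about 0. The hit rate is about 68-69% at both N = 44 and N = 68. That is close to the 69% and 66% for known fixed blocks of 4 and 6, so the gain is the loss of certainty, not of guessing.

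**The case against.** The strongest objection concerns the route to harm. Selection bias needs foresight and influence over entry together, and the protocol does not place both in one person. Most entry criteria in section 5 are rules: service date, a recent drinking episode or consequence, and an insomnia score threshold. The insomnia diagnosis is confirmed from time-stamped electronic diaries, research assistants do the contacting and scheduling, and randomization follows a finding of eligibility. The roughly two weeks between baseline interview and randomization also blur any prediction made at interview. All of this stands and limits the point to a risk.

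A reader might go further and infer that the unblinded person is the supervising psychologist and so also judges eligibility. The documents do not support this. Names are removed, so the identity cannot be established. The psychologist's role in the suicidal-ideation procedure, "who will make a clinical judgment regarding the continued level of care required", concerns the safety response, not study entry. The criterion excluding people who "have a severe or untreated psychiatric disorder that requires immediate clinical attention" leaves some room for judgement, but the protocol does not assign that judgement to the unblinded person.

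It is also fair to say that varying blocks may already be in use, and that any change now comes late: this is version 13, dated 29 December 2022, and Recruitment refers to existing participants in spring 2021.

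One part of the point survives all of this. Block-size access is expressly granted, the reason given does not require it, and no stated safeguard offsets it.

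**Conclusion.** The point holds as a cheap improvement, severity nice to have. If blocks are fixed at 2 to 6, between about 21% and 48% of allocations at N = 44 could be known with certainty by the person given the block size (about 22% to 49% at N = 68). Those ranges rest on an assumed fixed size, four strata at the protocol's prevalences, and independence of gender and PTSD. They describe what could be foreseen. They do not show that any enrolment decision was affected, and nothing in the documents says that this person makes such decisions.

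**What to change.** 1. In section 4, Blinding, delete block size from what this person may know. Knowledge of assignments can stay, since her task needs it.
2. For any remaining allocations, use randomly varying block sizes, with the sizes in use concealed from her and from everyone who screens or supervises.
3. Release each assignment to her only after eligibility is recorded as final.
4. State plainly that this removes certain prediction but leaves a best-guess rate of about 68-69% while past assignments are known. It therefore matters to name who decides eligibility and who holds the list.
5. For participants already randomized, report the block size, whether it was fixed, who held the list and who decided eligibility. If someone independent of enrolment already holds a concealed list, a sentence saying so settles most of the point.

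The cost is a few sentences and a revised list for remaining participants only. Sample size does not change. The protocol does not describe its randomization system, so whether the revised list needs any extra staff time cannot be judged from the text.
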